11.1. Adverse Events

AEs will be coded according to the MedDRA version 18.0 or higher. Unless otherwise specified, AEs will be summarized by SOC and PT, with SOCs presented in the standard international order and PTs within SOCs will be presented in descending order of subject incidence.

11.1.1. Overall Summary of TEAEs

An overall summary of the following TEAE categories will be provided for the Placebo-controlled Phase (Weeks 0 to 16):

- Any TEAE
- Any drug-related TEAE
- Any severe TEAE
- Any serious TEAE
- Any serious drug-related TEAE
- Any TEAE leading to drug interruption
- Any TEAE leading to drug withdrawal
- Any TEAE leading to death

In addition, for Apremilast Extension Phase (Weeks 16 to 32), Observational Follow-up Phase (4 weeks) and Apremilast Exposure Period overall summary of TEAEs will also be provided.

11.1.2. All TEAEs

All TEAEs will be summarized by SOC and PT as well as by PT only (in descending order of subject incidence). In addition to the Placebo-controlled Phase (Weeks 0 to 16) and the Apremilast-exposure Period, summaries will also be provided for the Apremilast Extension Phase (Weeks 16 to 32).

New events of all TEAEs by exposure interval (≤ 1 , > 1 to ≤ 4 , > 4 to ≤ 12 , and > 12 Weeks) will be summarized for the Placebo-controlled Phase. Each subject is counted once for either subject incidence or EAIR for each applicable specific TEAE in each exposure interval where an event started. The denominator of a subject incidence is the number of subjects with treatment duration exceeding the lower bound of the particular exposure interval, while the denominator of an EAIR is the sum of the exposure time during the exposure interval (up to the first event start date for subjects with at least one event starting in the interval) among the same number of subjects as in the denominator of the corresponding subject incidence.

In addition, new events of all TEAEs by exposure interval (≤ 1 , > 1 to ≤ 8 , > 8 to ≤ 16 , > 16 to ≤ 24 , > 24 to ≤ 32 Weeks) will be summarized for the Apremilast-exposure Period.

All TEAEs will be summarized by age category (< 65 , ≥ 65 years), sex, and race.

All TEAEs occurring after the date of the last dose of IP and up to 28 days after the last dose of IP will also be summarized by SOC and PT for subjects who enter the observational follow-up phase. The EAIR will not be provided in this summary.

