5.1.2. Apremilast-exposure Period for Safety Analysis

In addition to the above defined phases, Apremilast-exposure Period will be used for safety analyses.

- Apremilast-exposure Period:

This period starts on the date of either: (1) the first dose of IP following randomization (Week 0/Visit 2) for subjects who are treated with apremilast 30 mg BID first; or (2) the first dose of IP from the IP dispensed at Week 16/Visit 7 for subjects who were originally treated with placebo and are treated with apremilast 30 mg BID at Week 16.

This period stops on either: (1) data cut-off date; or (2) the day of the treatment discontinuation if the subject discontinued prior to or at Week 32/Visit 10; or (3) the last

known study day if the subject lost to follow-up prior to Week 32/Visit 10; or (4) Week 32/Visit 10 visit date.

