5.4. Time Points

Time points in all analyses are based on the remapped visits/study weeks using the following visit mapping algorithm, which may or may not be the same as the visits/study weeks as recorded in the database.

Post baseline time points in all analyses will be captured based on analysis visit window (range of study days) around the target day for each analysis visit, based on the actual day of evaluation relative to a reference date. Appropriate dates will be used to calculate the study day, e.g., date of measurement or date of specimen collection will first be used, and then the date of visits/study weeks as recorded in the database will be used. If there are multiple measurements within a time point based on the study day, then the non-missing value from the closest measurement to the planned study day will be used for that visit. If the value at a scheduled visit is missing and there is no value available within the time window based on the study day, the value at the study week will be missing.

Table 2: Table for Visit Mapping for by Time Point Analysis

Analysis Visit	Target Day	Visit Window
Baseline	1	≤ 1
Placebo-controlled Phase		
Week 2	15	2 – 21
Week 4	29	22 – 42
Week 8	57	43 – 70
Week 12	85	71 – 98
Week 16	113	99 – End of Phase
Apremilast Extension Phase		
Week 20	141	Start of Phase – 154
Week 24	169	155 – 196
Week 32	225	197 – End of Phase

Note: Target day and visit window are relative to the date of Visit 2/Week 0 (Day 1) for randomization. Definitions for baseline and start or end of the phases are specified in Section 5.1 and 5.3 for both efficacy and safety analysis.

Time points in the analyses or summaries of efficacy data over time include the scheduled study weeks per protocol, the end of a study phase, and the observational follow-up visit. Appropriate dates (e.g., date of measurement or date of specimen collection) will first be used to ensure only data (including data from scheduled, unscheduled, discontinuation, and observational follow-up visits) measured or collected within the specific analysis phase (as defined in Section 5.1) being analyzed or summarized are included, and then the visits/study weeks as recorded in the database will be used to assign one value (possibly missing) to each time point at the subject level. It is possible that multiple assessment values will fall into the same visit window. The following rule may be used to select the unique value for that analysis visit:

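### For subjects on apremilast from Week 0, the last adverse-event exposure interval closes at 224 days, while the Apremilast-exposure Period can run to Day 229

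*SAP*

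**What the plan says.** SAP 11.1.2 sets five exposure intervals for the Apremilast-exposure Period, with breaks at 1, 8, 16, 24 and 32 weeks. The last is closed above ("> 24 to ≤ 32 Weeks) will be summarized for the Apremilast-exposure Period") and no later interval is given. The matching list for the Placebo-controlled Phase, in the same section, ends open: "and > 12 Weeks) will be summarized for the Placebo-controlled Phase". SAP 11.1.4 carries the same intervals over to drug-related TEAEs.

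SAP 5.1.2 defines the period being divided. It starts at "the first dose of IP following randomization (Week 0/Visit 2) for subjects who are treated with apremilast 30 mg BID first", or at "the first dose of IP from the IP dispensed at Week 16/Visit 7 for subjects who were originally treated with placebo". For a subject who completes, it stops at the "4) Week 32/Visit 10 visit date".

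SAP Table 2 (section 5.4) gives Week 32 a target of Day 225 and an analysis window of "197 – End of Phase", so there is no numeric upper limit. A note fixes the origin: "Target day and visit window are relative to the date of Visit 2/Week 0 (Day 1) for randomization". Protocol 6.2 and the Table of Events allow 4 days either side of each treatment-phase visit.

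**The concern.** A set of exposure intervals should cover the whole period that it summarises. Here the period can outlast its last interval by design, without any protocol deviation. A programmer who follows SAP 11.1.2 literally would have no cell for an event that starts after 224 days of exposure but on or before Visit 10, and would leave it out.

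At stake is the count in the longest-exposure interval. SAP 11.1.2 puts in the incidence denominator every subject whose treatment lasted beyond the interval's lower bound. A subject treated beyond 24 weeks therefore stays in the denominator even if that subject's only late event is left out of the numerator.

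**Working it through.** **Inputs.** Interval limit of 32 weeks (SAP 11.1.2). Week 32 target of Day 225 (SAP Table 2). Visit window of ± 4 days (protocol 6.2). First dose is Day 1 (SAP Appendix A3). Exposure up to an event includes the event's start date (SAP 11, definition of the exposure-adjusted incidence rate, EAIR). About 300 subjects randomised 2:1 (SAP 4.4).

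**Reproducing Table 2.** Target day = 7 × week + 1. For Weeks 2, 4, 8, 12, 16, 20, 24 and 32 this gives 15, 29, 57, 85, 113, 141, 169 and 225, which matches every entry. Visit 10 is therefore permitted on Days 221 to 229, which is nine days.

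**Interval limit.** 32 × 7 = 224 days. The last interval is (32 − 24) × 7 = 56 days long.

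**Apremilast from Week 0, first dose on Day 1.** SAP 11.1.2 gives no formula for week of onset, so both usual counts are shown.

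| Event start | Inclusive: day ÷ 7 | Elapsed: (day − 1) ÷ 7 |
|---|---|---|
| Day 224 | 32.00, last interval | 31.86, last interval |
| Day 225 | 32.14, none | 32.00, last interval |
| Day 226 | 32.29, none | 32.14, none |
| Day 229 | 32.71, none | 32.57, none |

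Of the nine permitted days, five are uncovered on the inclusive count and four on the elapsed count.

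**First dose one day after randomisation.** Both counts shift by a day. Day 225 is then covered on either count, Day 226 is uncovered only on the inclusive count, and Day 229 is uncovered on both.

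**Placebo first.** With a first apremilast dose on Day 113, Visit 10 on Day 225 is 225 − 113 + 1 = 113 days, or 16.14 weeks inclusive (16.00 elapsed). Visit 10 on Day 229 is 117 days, or 16.71 weeks (16.57 elapsed). For first doses from Day 109 to Day 118 and Visit 10 from Day 221 to Day 229, the inclusive range is 104 to 121 days, or 14.86 to 17.29 weeks. All of these fall in the 8-to-16 or the 16-to-24 week interval, so there is no gap.

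**Size.** About 300 × 2/3 = 200 subjects start on apremilast, and only those who reach Visit 10 can be affected. If visit dates are spread evenly over the nine days and dosing continues to the visit:

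- Inclusive count: (1 + 2 + 3 + 4 + 5)/9 = 1.67 days per completer; 1.67/56 = 3.0%.
- Elapsed count: (1 + 2 + 3 + 4)/9 = 1.11 days per completer; 1.11/56 = 2.0%.

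**The case against.** The best defence is that these are intervals of exposure and planned treatment is 32 weeks. SAP 9.1.3 ends treatment duration at the last apremilast dose, not at the visit. If the last dose is on Day 224 and the visit on Day 225, exposure is exactly 32 weeks. An event at the visit is then post-dose, and SAP 11.1.2 has a separate summary of TEAEs after the last dose, up to 28 days, for subjects who enter follow-up. The documents do not say whether a dose is taken on the day of Visit 10. The inclusive count is also written for the EAIR, not as the rule for placing an event in an interval.

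Part of this stands. The on-time visit on Day 225 is uncovered only under the inclusive count from a Day 1 first dose, and the mean uncovered time depends on dosing up to the visit. It does not remove the point. SAP 5.1.2 runs the period to the visit date whatever the last dose date. Late visits on Days 226 to 229 are uncovered on both counts when the first dose is on Day 1. The post-dose summary is a different table, and it excludes an event that starts on the last-dose date.

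A reader might infer that final-visit events are lost for all subjects. They are not, because placebo-first subjects have only about 15 to 17 weeks of exposure at Visit 10. A reader might also infer that the event rate in the last interval is pulled down. The EAIR denominator counts only exposure time inside the interval, so the uncovered days leave it together with their events. A bias in the EAIR would need onset dates to cluster at the visit. Visit 10 does include laboratory tests, a physical examination and adverse-event evaluation, but nothing in the documents says how often onset is dated that day.

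**Conclusion.** The closed limit is wrong as written for subjects on apremilast from Week 0, and the consequence is small. With a first dose on Day 1, events starting on Days 226 to 229 have no interval, and events on Day 225 have none under the inclusive count. The uncovered time is about 2 to 3% of the last interval, assuming evenly spread visits and dosing up to the visit. A visit later than the permitted window would widen the gap, since Table 2 sets no upper limit.

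Subject incidence in the last interval can be slightly understated. The number of events cannot be estimated, because the documents give no event rates. The effect is confined to the by-interval tables for all TEAEs and for drug-related TEAEs in this period. The overall TEAE tables are unchanged, and the by-interval table for serious TEAEs (SAP 11.1.6) is specified only for the Placebo-controlled Phase, whose last interval is open. Safety reporting is descriptive, so no test or efficacy result is involved. This is a low-priority correction.

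**What to change.** In SAP 11.1.2, replace the last Apremilast-exposure interval with an open one, > 24 Weeks, in line with the open > 12 Weeks interval for the Placebo-controlled Phase. State that it is limited to events that start within the Apremilast-exposure Period of SAP 5.1.2, and that exposure time is counted to the end of treatment. Add one sentence that defines how week of onset is counted, inclusive or elapsed, and from which date. SAP 11.1.4 then follows by its cross-reference. Every permitted Visit 10 day from 221 to 229 falls in an interval under either count. The cost is a few words in the SAP and the table shells, with no new data and no change to study conduct.

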11.1.3. Common TEAEs

TEAEs with subject incidence $\geq 5\%$ (or another cut-off if justified) in any treatment group will be summarized by SOC and PT as well as by PT only in descending order of subject incidence.

11.1.4. Drug-related TEAEs

Drug-related TEAEs will be summarized and new events of drug-related TEAEs by exposure interval (see Section 11.1.2) will be summarized.

11.1.5. TEAEs by Maximum Severity

All TEAEs will be summarized by maximum severity (mild, moderate, severe, and, if needed, missing). If a subject reports multiple occurrences of a specific event within a specific analysis phase or period, the subject will be counted only once by the maximum severity. If the severity is missing for one or more of the occurrences, the maximum severity of the remaining occurrences will be used. If the severity is missing for all of the occurrences, the subject will be counted only once in the “missing” category of severity.

11.1.6. Serious TEAEs

Serious TEAEs and serious drug-related TEAEs will be summarized.

New events of serious TEAEs and serious drug-related TEAEs by exposure interval will be summarized for Placebo-controlled Phase (Weeks 0 to 16).

Serious TEAEs will be summarized by age category (< 65 , ≥ 65 years), sex and race.

A subject data listing of all serious AEs (both TEAEs and non-TEAEs) will be provided.

11.1.7. TEAEs Leading to Drug Interruption and TEAEs Leading to Drug Withdrawal

TEAEs leading to drug interruption and TEAEs leading to drug withdrawal will be summarized.

TEAEs leading to drug withdrawal will also be summarized by age category (< 65 , ≥ 65 years), sex and race.

A subject data listing of TEAEs leading to drug withdrawal will be provided.

11.1.8. Deaths

TEAEs leading to death will be summarized. A subject data listing of all deaths will be provided.

11.2. Psoriasis Flare

Psoriasis flare represents an atypical or unusual worsening of disease during treatment (Carey, 2006). It is defined as a sudden intensification of psoriasis requiring medical intervention or a diagnosis of new generalized erythrodermic, inflammatory, or pustular psoriasis. At any time, a psoriasis flare may be reported as an adverse event, provided it meets the protocol definition.

TEAEs in their coded terms containing psoriasis will be summarized. A subject data listing of all those adverse events will be provided.

11.3. Clinical Laboratory Evaluations

The endpoints for clinical laboratory evaluations include:

- Laboratory marked abnormalities (see [Appendix A2](#))
- Observed value and change from baseline over time in the following laboratory parameters
 - Hematology: hemoglobin, hematocrit, platelet, erythrocytes, leukocytes, basophils/leukocytes, eosinophils/leukocytes, lymphocytes/leukocytes, monocytes/leukocytes, neutrophils/leukocytes, basophils, eosinophils, lymphocytes, monocytes, and neutrophils
 - Serum chemistry: glucose, lactate dehydrogenase (LDH), bicarbonate, calcium, chloride, potassium, magnesium, phosphate, sodium, blood urea nitrogen, creatinine, urate, total cholesterol, high-density lipoprotein cholesterol (HDL-C), low-density lipoprotein cholesterol (LDL-C), triglycerides, alkaline phosphatase, AST (SGOT), ALT (SGPT), total bilirubin, albumin, and total protein
- Shifts from baseline to post-baseline time points and to the worst post-baseline value in terms of normal/abnormal (low or high) in the above hematology and serum chemistry parameters

Summary statistics of observed values and changes from baseline in laboratory parameters will be provided over time. Frequency summaries (shift tables) of shifts from baseline to post-baseline time points and to the worst post-baseline value in terms of normal/abnormal will be provided.

Laboratory marked abnormalities will be summarized; subject incidence and EAIR for each abnormality will be calculated based on subjects with a baseline value and at least one post-baseline value for criteria requiring baseline or subjects with at least one post-baseline value for criteria not requiring baseline. A subject data listing of laboratory marked abnormalities will be provided. Laboratory marked abnormalities will also be summarized for subjects with normal values at baseline and for subjects with abnormal values at baseline separately. For the purposes of these summaries, subjects with abnormal (normal) values at baseline are defined as those whose baseline value is low (not low) for criteria concerning low values and those whose baseline value is high (not high) for criteria concerning high values; both low and high are relative to the laboratory normal range.

A subject data listing of all laboratory data, including urinalysis, will be provided.

11.4. Vital Signs and Weight

The endpoints for vital signs and weight include:

- Observed value and change from baseline over time in vital signs (temperature, pulse, and blood pressure)
- Shifts from baseline to post-baseline time points and to the worst post-baseline value in terms of normal/abnormal in pulse and blood pressure (normal ranges are defined as: 60-100 beats/minute for pulse, 90-140 mmHg for systolic blood pressure, and 60-90 mmHg for diastolic blood pressure)

- Observed value, change and percent change from baseline over time in weight

Summary statistics of observed values and changes from baseline in vital signs (including weight, for which percent change from baseline will also be summarized) will be provided over time. Frequency summaries (shift tables) of shifts from baseline to post-baseline time points and to the worst post-baseline value in terms of normal/abnormal will be provided for pulse and blood pressure.

Frequency summaries of change and percent change in weight from baseline to the end of the period will be provided by baseline BMI category (< 25 , ≥ 25 to < 30 , ≥ 30 to < 35 , ≥ 35 to < 40 , and ≥ 40 kg/m²) and by baseline weight category (< 70 , ≥ 70 to < 85 , ≥ 85 to < 100 , and ≥ 100 kg). The categories of weight change (kg) and percent change (%) are < -20 , ≥ -20 to < -10 , ≥ -10 to < -5 , ≥ -5 to < 0 , 0 , > 0 to ≤ 5 , > 5 to ≤ 10 , > 10 to ≤ 20 , and > 20 . The end-of-period or end-of-phase value is the last post-baseline value in the analysis period or phase (excluding the value obtained at the follow-up visit, if applicable) up to 28 days after the last dose of IP in the study.

A subject data listing of all vital signs and weight data will be provided.

11.5. Physical Examination

A complete physical examination includes evaluations of skin, nasal cavities, eyes, ears, lymph nodes, and respiratory, cardiovascular, gastrointestinal, neurological, and musculoskeletal systems. The complete physical examination is done at screening and at the Early Termination or Last Treatment Visit (Visit 10).

The protocol specified that physical examination findings of clinical significance (as defined by the investigator) are to be reported as AEs. No summary of physical examination findings will be provided.

REFERENCES

CCI

SAS Institute Inc. 2015. SAS/STAT® 14.1 User's Guide. Cary, NC: SAS Institute Inc.

Mehrotra, DV, and Railkar, R. Minimum risk weights for comparing treatments in stratified binomial trials. *Statist. Med.*, 2000; 19: 811–825.

Appendix A1 – Conventions related to dates

Following are the general conventions for various computations and imputations for references. Users may need to consult with study team for specific study practices or regulatory guidelines.

A1.1 Guideline of Partially Missing Date Imputation

A1.1.1 Adverse Events

Partially missing AE start dates will be imputed in the ADaM dataset for AEs, but partially missing AE end dates will not be imputed in the same dataset. If the AE end date is complete with no missing year, month, or day, and the partially missing start date imputed by the rules below is after the AE end date, then the start date will be imputed by the AE end date.

Subjects who were treated with apremilast at Week 0/Visit 2

The principle of the imputation rules for subjects who were treated with apremilast initially is to treat the AE as treatment-emergent, i.e., occurring on or after the date of the first dose of IP, if possible.

Let an AE start date be represented as “ $D_{Event}/M_{Event}/Y_{Event}$ ”, and the date of the first dose of IP as “ $D_{IP}/M_{IP}/Y_{IP}$ ”. The following table gives the imputation rules for partially missing AE start dates for subjects who were treated with apremilast initially.

Table 4: Imputation Rules for Partially Missing AE Start Dates for Subjects Who Were Treated with Apremilast Initially

Scenario	Condition	Imputation Rule
Partially missing date includes year only (both month and day are missing)		
1	$Y_{Event} < Y_{IP}$	12/31/ Y_{Event}
2	Otherwise, i.e., $Y_{IP} \leq Y_{Event}$	Max (date of first dose of IP, 1/1/ Y_{Event})
Partially missing date includes both year and month (only day is missing)		
1	$Y_{Event} < Y_{IP}$, or ($Y_{Event} = Y_{IP}$ and $M_{Event} < M_{IP}$)	Last date of M_{Event}/Y_{Event}
2	Otherwise, i.e., $Y_{IP} < Y_{Event}$, or ($Y_{IP} = Y_{Event}$ and $M_{IP} \leq M_{Event}$)	Max (date of first dose of IP, 1/ M_{Event}/Y_{Event})

Subjects who were treated with placebo at Week 0/Visit 2

The principle of the imputation rules for subjects who were treated with placebo initially and started apremilast treatment at Week 16 is to consider the AE starting on or after the date of the first dose of apremilast, if possible; if the partially missing start date suggests that it is prior to the date of the first dose of apremilast, the AE will be considered starting on or after the date of the first dose of IP, if possible.

The following are 4 scenarios considered in the imputation rules:

1. The partially missing AE start date suggests the date is prior to the date of the first dose of IP: impute it by the latest possible date (determined by the non-missing field of the date);
2. The partially missing AE start date suggests the date is after the date of the first dose of apremilast following Week 16: impute it by the earliest possible date (determined by the non-missing field of the date);
3. The partially missing AE start date is in the same year (if both month and day are missing), or the same year/month (if only day is missing) of the first dose of apremilast following Week 16: impute it by the date of the first dose of apremilast;
4. The partially missing AE start date suggests the date is no earlier than the date of the first dose of IP but prior to the date of the first dose of apremilast following Week 16: impute it by the date of the first dose of IP, or the earliest possible date (determined by the non-missing field of the date), whichever occurs later.

Let an AE start date be represented as " $D_{Event}/M_{Event}/Y_{Event}$ ", the date of the first dose of IP as " $D_{IP}/M_{IP}/Y_{IP}$ ", and the date of the first dose of apremilast following Week 16 as " $D_{APR}/M_{APR}/Y_{APR}$ ". The following table gives the imputation rules for partially missing AE start dates.

Table 5: Imputation Rules for Partially Missing AE Start Dates for Subjects Who Were Treated with Placebo Initially

Scenario	Condition	Imputation Rule
Partially missing date includes year only (both month and day are missing)		
1	$Y_{Event} < Y_{IP}$	12/31/ Y_{Event}
2	$Y_{Event} > Y_{APR}$	1/1/ Y_{Event}
3	$Y_{Event} = Y_{APR}$	Date of first dose of apremilast following Week 16
4	Otherwise, i.e., $Y_{IP} \leq Y_{Event} < Y_{APR}$	Max (date of first dose of IP, 1/1/ Y_{Event})
Partially missing date includes both year and month (only day is missing)		
1	$Y_{Event} < Y_{IP}$, or ($Y_{Event} = Y_{IP}$ and $M_{Event} < M_{IP}$)	Last date of M_{Event}/Y_{Event}
2	$Y_{Event} > Y_{APR}$, or ($Y_{Event} = Y_{APR}$ and $M_{Event} > M_{APR}$)	1/ M_{Event}/Y_{Event}
3	$Y_{Event} = Y_{APR}$ and $M_{Event} = M_{APR}$	Date of first dose of apremilast following Week 16
4	Otherwise, i.e., $Y_{IP} < Y_{Event} < Y_{APR}$, or ($Y_{IP} = Y_{Event} < Y_{APR}$ and $M_{IP} \leq M_{Event}$), or ($Y_{IP} = Y_{Event} = Y_{APR}$ and $M_{IP} \leq M_{Event} < M_{APR}$), or ($Y_{IP} < Y_{Event} = Y_{APR}$ and $M_{Event} < M_{APR}$)	Max (date of first dose of IP, 1/ M_{Event}/Y_{Event})

A1.1.2 Prior/Concomitant Medications/Procedures

Partially missing start/stop dates for prior/concomitant medications and partially missing start dates for prior/concomitant procedures will be imputed in the ADaM dataset for prior/concomitant medications/procedures. For prior/concomitant medications, if the stop date is complete with no missing year, month, or day, and the partially missing start date imputed by the rule below is after the stop date, then the start date will be imputed by the stop date.

Partially missing prior/concomitant medication/procedure start dates will be imputed by the earliest possible date given the non-missing field(s) of the date.

Partially missing prior/concomitant medication stop dates will be imputed by the latest possible date given the non-missing field(s) of the date.

A1.1.3 Medical History

Partially missing medical history start dates will be imputed in the ADaM dataset for medical history (for the purposes of calculating durations of PsA and psoriasis). The 16th of the month will be used to impute a partially missing start date that has only the day missing, and July 1st will be used to impute a partially missing start date that has both the month and day missing.

A1.1.4 Treatment Duration

Partially or completely missing last dose dates will be imputed in the ADaM dataset for treatment duration.

When partially missing last dose date is available, set last dose date to the maximum of [the earliest possible date given the non-missing field(s) of last dose date, the minimum of (the latest possible date given the non-missing field(s) of last dose date, last known date in database, first non-missing Early Termination (ET) visit date)]

When last dose date is completely missing, set last dose date to the minimum of (last known date in database, first non-missing Early Termination (ET) visit date)

Last known date in database is defined as maximum of (last visit date, lab, vital signs, ECG assessment date, AE start or end dates, concomitant medications start or end dates, concomitant procedure date, last dose date from 'Disposition-Treatment' page, treatment exposure start or end dates where doses were completely or partially taken, death date).

